5.2.3 Safety Analysis Set

The safety analysis set (SafAS) is defined for each dose as the subset of subjects having received this dose. Any subject who receives a dose will be analyzed according to the treatment received at this dose and after any dose according to the vaccine received at the first dose.

Safety data recorded for a vaccine received out of the protocol design will be excluded from the analysis (and listed separately). Thus, if a subject does not receive any vaccine at a given visit or if the vaccine received does not correspond to any protocol group at a specific dose, the subject is excluded from the SafAS at this dose, however, this subject will be included in the analysis for all doses combined (referred to as analysis "after any dose") according to the first dose received that corresponds to a protocol group.

5.2.4 Populations Used in Analyses

Immunogenicity analyses will be performed on the FAS, according to the randomized vaccine group. The main immunogenicity analyses will also be performed on the PPAS, according to the injected group.

Safety analyses will be performed on the SafAS, according to the injected vaccine group.

5.3 Handling of Missing Data and Outliers

5.3.1 Immunogenicity

No replacement will be done as the degree of missing data is expected to be very low.

5.3.2 Safety

No replacement will be done as the degree of missing safety data is expected to be very low.

Missing data in vaccine studies are mostly due to dropouts. The dropouts due to AEs or lost to follow-up subjects will be identified and discussed in the study report.

5.3.2.1 Immediate

For unsolicited non-serious systemic AEs, a missing response to the “Immediate” field is assumed to have occurred after the 30-minute surveillance period and will not be imputed.

For SAEs, missing or partially missing elapsed time from last injection (recorded if within 24 hours) will remain missing and will not be imputed.

5.3.2.2 Causality

Missing causality (relationship) for unsolicited non-serious AEs and SAEs will be considered at the time of analysis as related to vaccination.

5.3.2.3 Measurements

Partially missing temperatures will be handled as described in Section 4.3.1.1.1.

5.3.2.4 Intensity

For solicited reactions, missing intensities will be handled as described in Section 4.3.1.1.1.

5.3.2.5 Start Date and Stop Date

Missing or partially missing start dates for unsolicited AEs will remain missing and will not be imputed.

Missing or partially missing stop dates for AEs (solicited reactions and unsolicited AEs) will remain missing and will not be imputed.

If either the start or stop date is missing or partially missing, the time of onset will be considered to be missing. Nevertheless unsolicited AEs with missing time of onset will be included in analyses according to the visit collected.

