Subjects are to measure body temperature once per day, preferably always at the same time. The optimal time for measurement is the evening, when body temperature is the highest. Temperature is also to be measured at the time of any apparent fever. The observed daily temperature and the route of measurement are to be recorded in the DC/MA, and the highest temperature will be recorded by the site in the CRF. The preferred route for this trial is oral. Pre-vaccination temperature is also systematically collected on the source document. Tympanic thermometers must not be used.

9.2.3.3 Unsolicited Non-serious Adverse Events From Day 0 to Day 28 After Each Vaccination

In addition to recording solicited reactions, subjects will be instructed to record any other medical events that may occur between each vaccination and during the 28-day period after the last vaccination. Space will be provided in the diary card for this purpose.

For each unsolicited non-serious AE, the following information is to be recorded:

- Start and stop dates^a
- Intensity of the event:
 - For measurable unsolicited non-serious AEs that are part of the list of solicited reactions, the size of the AE as well as the temperature for fever will be collected and analyzed based on the corresponding scale used for solicited reactions (see [Table 9.1](#) and [Table 9.2](#))
 - Other unsolicited non-serious AEs will be classified according to the following intensity scale:
 - Grade 1: No interference with activity
 - Grade 2: Some interference with activity
 - Grade 3: Significant; prevents daily activity
- Action taken for each AE, if any (e.g., medication)

The action taken by the subject to treat any **unsolicited AEs** will be classified in the CRF using the following scale:

0: None

1: Medication (self-medication with an existing prescription or over-the-counter medication)

2: Health care provider contact (no new medication prescribed)

^a The stop date of all related AEs will be actively solicited. For other events, the investigator will provide the stop date when it becomes available. AEs for which no stop date was obtained during the course of the trial will be considered as ongoing at the end of the trial.

3: Health care provider contact and prescription of a new medication (health care provider instructed subject to take a new medication, either an over-the-counter medication or one requiring a written prescription)

- Whether the AE led to study discontinuation

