2) For non-measurable solicited reactions, daily intensities will correspond to daily records reported in the clinical database. For measurable solicited reactions the daily measurements reported in the clinical database will be converted based upon the intensity scales defined in the protocol; this assumes a reaction that is too large to measure (not measurable [NM]) is Grade 3. Note the intensity could be considered "None" (not a reaction) in the analysis despite being considered a reaction by the investigator (e.g., swelling measurement > 0 mm but < 25 mm in adults).

Note: The maximum intensity on the ongoing period is derived from the record of the maximum intensity/measurement after the end of the solicited period following the rule described above.

4.3.1.1.2 **Maximum Overall Intensity**

Maximum overall intensity is derived from the daily intensities computed as described in Section 4.3.1.1.1 and is calculated as the maximum of the daily intensities over the period considered.

4.3.1.1.3 **Presence**

Presence is derived from the maximum intensity on the period considered:

- None: no presence
- Grade 1, Grade 2, or Grade 3: presence
- Missing: missing presence

Subjects with at least one non-missing presence for a specific endpoint will be included in the analysis. Conversely, those subjects without non-missing presence will not be included in the analysis of the endpoint.

4.3.1.1.4 **Time of onset**

Time of onset is derived from the daily intensities computed as described in Section 4.3.1.1.1. It corresponds to the first day with intensity of Grade 1, Grade 2, or Grade 3.

Note: If a reaction is not continuous (i.e., reaction occurs over two separate periods of time intervened by at least one daily intensity Missing or None) then the time of onset is the first day of the first occurrence.

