4.3.1.1.6 Overall Number of Days of Occurrence

If a reaction is ongoing at the end of the solicited period, then the overall number of days of occurrence is derived from the daily intensities and the stop date of the reaction after the end of the solicited period. The overall number of days of occurrence is:

- (stop date – last vaccination date) + (number of days of occurrence within the solicited period) – length of the solicited period + 1

If the stop date is missing or incomplete (contains missing data [MD]), the overall number of days of occurrence will be considered as “Missing”.

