4.3.1.2.4 Time of onset

Time of onset is derived from the start date of the unsolicited non-serious AE provided in the clinical database and the date of last vaccination:

- start date of the unsolicited non-serious AE – date of previous vaccination

The time of onset should be considered as missing only if one or both of the dates are missing or partially missing.

An AE with missing time of onset will be considered to have occurred just after the vaccination indicated by the visit number, so will be included in these tables. Note: Unsolicited non-serious AE that occurred before vaccination (negative time of onset) will not be included in analysis, but will be listed separately.

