4.3.1.2.5 Duration

Duration is derived from the start and stop dates of the unsolicited non-serious AE provided in the clinical database:

- stop date of unsolicited non-serious AE - start date of unsolicited non-serious AE + 1.

The duration should be considered as missing only if one or both of the start and stop dates of the unsolicited non-serious AE is missing or partially missing.

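### SAP 5.3.2.5 makes AE time of onset missing when only the stop date is missing, contradicting the onset derivation in SAP 4.3.1.2.4

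*SAP*

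**What the plan says.** **The rule at issue.** SAP 5.3.2.5 says that missing start and stop dates are not imputed, and then: "If either the start or stop date is missing or partially missing, the time of onset will be considered to be missing". It goes on: "Nevertheless unsolicited AEs with missing time of onset will be included in analyses according to the visit collected".

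**The onset derivation.** SAP 4.3.1.2.4 defines onset of an unsolicited non-serious AE as AE start date minus previous vaccination date, and adds: "The time of onset should be considered as missing only if one or both of the dates are missing or partially missing".

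**Where the SAP otherwise uses the stop date.**
- Duration of unsolicited AEs, in SAP 4.3.1.2.5, where the condition is an absent or partial date: "The duration should be considered as missing only if one or both of the start and stop dates of the unsolicited non-serious AE".
- Overall days of occurrence of a solicited reaction, in SAP 4.3.1.1.6, where the result is then set to Missing: "If the stop date is missing or incomplete (contains missing data [MD]), the overall number of days of occurrence will be considered as".

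Onset of a solicited reaction (SAP 4.3.1.1.4) is read from the daily intensities: "It corresponds to the first day with intensity of Grade 1, Grade 2, or Grade 3".

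**Where onset is reported.** SAP 5.1.2.2.1 presents unsolicited non-serious AEs after any and each injection by time of onset, with rows Missing, D0-D3, D4-D7, D8-D14 and D15 or later.

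**Collection of stop dates.** A footnote to Protocol 9.2.3.3 says: "The stop date of all related AEs will be actively solicited. For other events, the investigator will provide the stop date when it becomes available". It adds that AEs with no stop date obtained during the trial count as ongoing at its end.

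**The concern.** For one type of AE the SAP prescribes two different onset values. No onset derivation in the SAP needs a stop date, so the extra condition in 5.3.2.5 can only discard a known value. The start-or-stop condition is the one that belongs to duration, and it may have been carried into the onset sentence by mistake, although the documents do not say so.

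At stake is the onset distribution of unsolicited AEs. If the 5.3.2.5 rule is applied, an AE's row depends on whether someone later recorded when it ended, which has nothing to do with when it began.

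**Working it through.** The documents give no figure to reproduce. The check is to apply both rules as written to the same AEs.

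**Inputs**
- Rule A (SAP 4.3.1.2.4): onset = start date − previous vaccination date; missing only if one of these is missing or partial.
- Rule B (SAP 5.3.2.5): onset missing if the start or the stop date is missing or partial.
- Rows: SAP 5.1.2.2.1, as listed above.
- Vaccination days: D14 for VAC4 and D28 for VAC5, from the schedule in both documents.

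**Hypothetical AEs, vaccination date known**

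| AE | Onset (start − vaccination) | Row under A | Row under B |
|---|---|---|---|
| Starts 5 days after a dose, stop known | 5 | D4-D7 | D4-D7 |
| Starts 5 days after a dose, no stop | 5 | D4-D7 | Missing |
| Starts D24, after VAC4, no stop | 24 − 14 = 10 | D8-D14 | Missing |
| Starts D50, after VAC5, no stop | 50 − 28 = 22 | D15 or later | Missing |
| No start date, stop known | not computable | Missing | Missing |

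The rules differ only when the start date is known and the stop date is not.

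**Can the two be reconciled?** In 4.3.1.2.4 the dates meant are the two in the formula directly above the sentence, so the stop date is not one of them, and its *only if* excludes any further condition. Reading 5.3.2.5 as meant for solicited reactions does not help either: their onset needs no stop date, and the next sentence of 5.3.2.5 concerns unsolicited AEs.

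**What does not move.** Under 5.3.2.5 an AE with missing onset stays in the analysis by visit, and SAP 4.3.1.2.3 assigns the last vaccination from the visit number first. The denominator is the number vaccinated (SAP 5.1.2.2.1). Incidence, intensity, causality and SOC/PT counts are therefore the same under either rule. Duration is missing under both, correctly.

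**Scale per affected subject.** At planned group sizes, and if the subject has no other AE in the same onset row, 1/80 = 1.25 points (VRVg-2 groups) or 1/40 = 2.5 points (VRVg-1, Imovax Rabies) leaves a known onset row. The number of such subjects cannot be derived, because the documents give no rate of missing stop dates.

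**The case against.** **The strongest defence.** SAP 4.3.1.2.4 is the dedicated derivation section. It gives the formula and says *only if*, so a programmer who follows it gets the right row. This stands in part: the loss of the onset category is conditional on 5.3.2.5 being programmed. But 5.3.2.5 is the section on missing dates, and nothing in the SAP says which rule prevails.

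**Few AEs are exposed.** Protocol 9.2.3.3 asks for start and stop dates for every unsolicited non-serious AE and actively seeks them for related ones. Injection site AEs are related by convention, so mainly unrelated systemic AEs remain. Whether an AE recorded as ongoing counts as having a missing stop date depends on eCRF conventions that are not in the documents. Both points limit the size without removing the contradiction. Time of onset is also not a headline endpoint: Protocol 9.2.2 names it among items that could be described.

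**Stronger readings that the documents do not support**
- *AEs escape exclusion.* SAP 4.3.1.2.4 says "An AE with missing time of onset will be considered to have occurred just after the vaccination indicated by the visit number". A reader might infer that AEs starting before vaccination, or more than 28+3 days after it, would be kept once their onset is set to missing. But 4.3.1.2.4 sets aside AEs that occurred before vaccination, and 5.1.2.2.1 counts those occurring after the injection and lists late ones separately. A known start date still settles each of these.
- *AEs noted at V06 have no dose.* The dose-5 period in SAP 5.1.2.2.1 names only V07. But no injection follows VAC5, and diary card 3, checked at V06, is collected at V07, so such AEs can only belong to dose 5.
- *The vaccine comparison is biased.* Stop-date collection differs by causality, but nothing in the documents shows that it differs by vaccine group.

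**Conclusion.** The contradiction is real, and SAP 5.3.2.5 is wrong as written. If it is the rule programmed, an unsolicited AE with a known start date and no stop date is tabulated as Missing instead of in its known onset row. This assumes that a stop date never obtained is handled as missing in the database. The number of AEs affected is unknown.

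Severity is minor. The effect is confined to the onset presentation within a descriptive safety analysis with no hypothesis test, and it does not threaten the trial's conclusions.

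**What to change.** In SAP 5.3.2.5, delete *or stop* from the onset sentence. A missing or partial stop date then makes only duration missing (4.3.1.2.5), and onset is missing only under 4.3.1.2.4.

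Three separate editorial corrections can go into the same revision; they do not bear on the main point:
- SAP 4.3.1.3.1 sends SAE last vaccination to 4.3.1.2.4, the onset section; it should cite 4.3.1.2.3.
- SAP 4.3.1.3.2 sends SAE time of onset to 4.3.1.2.5, the duration section; it should cite 4.3.1.2.4.
- In SAP 5.1.2.2.1, the footnotes for subjects who stop after the third and fourth injections count 28 days from the first and second injections, whereas the first two footnotes count from the injection after which vaccination stopped. These need to be reconciled.

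Cost: SAP wording, plus the onset derivation code if it was written to 5.3.2.5. No new data are needed.

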5.3.3 Efficacy

Not applicable.

5.4 Interim/Preliminary Analysis

No formal interim analyses are planned.

The statistical analysis will be performed in two steps. A first statistical analysis will be performed when results on all immunogenicity and safety data collected up to D56 (i.e., up to 28

[figure not shown]
days after the primary vaccination series) will be obtained and locked. A final statistical analysis will be performed when immunogenicity and safety results from D56 to M7 will be obtained and locked.

5.5 Determination of Sample Size and Power Calculation

An arbitrary number of 80 subjects per VRVg-2 group and 40 subjects in both VRVg-1 and Imovax Rabies has been proposed.

Table 5.4:

In terms of safety, according to the occurrence rate of the observed AEs, 80 subjects will allow for the following 95% CI (Table 5.5).

95% CI calculations corresponding to anticipated AEs rates in VRVg-2 groups of 80 subjects.

Table 5.5: 95% CI calculations corresponding to anticipated AEs rates in VRVg-2 groups of 80 subjects

| Observed numbers | Observed % | 95% CI |
|------------------|------------|--------------|
| 8/80 | 10.0 | (4.4; 18.8) |
| 12/80 | 15.0 | (8.0; 24.7) |
| 16/80 | 20.0 | (11.9; 30.4) |
| 20/80 | 25.0 | (16.0; 35.9) |
| 24/80 | 30.0 | (20.3; 41.3) |

5.6 Data Review for Statistical Purposes

A treatment blind review of the data has been anticipated through the data review process led by data management before database lock. This review of the data included a statistical review.

